Document Date: 03/25/2019

The Effects of a Jump Rope Exercise Program on Vascular Health, Inflammatory Markers in Prehypertensive Adolescent Girls: full study protocol and statistical analysis plan

NCT#03534427

Study protocol

Participants

Forty girls (age 14-16) volunteered to participate in this research study. All participants were classified as prehypertensive (120-140 mmHg systolic BP and/or 80-90 mmHg diastolic BP) and had abdominal obesity (waist > 80 cm, BMI equal to or greater than the 95th percentile for age and sex). All participants were considered to be inactive, meaning they participated in less than 1 hour of regular physical activity per week within the last 6 months. Other exclusion criteria included a previous musculoskeletal injury within the last year that may negatively affect participation, as well as cardiovascular, pulmonary, adrenal, pituitary, and thyroid diseases. Participants who were already involved in a regular exercise program, on daily medication(s), including antioxidants and fat loss supplements, or weight loss diet plans were also excluded from participation. All procedures performed in this study were in accordance with the ethical standards of the institutional research committee at Pusan National University (PNU IRB/2016_105_HR) and with the tenets of the Declaration of Helsinki. This study was registered in Clinicaltrials.gov (NCT03534427). Informed consent was obtained from all individual participants and their parent/guardian(s) included in this study. Participant characteristics can be seen in Table 1.

Study design

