A two-armed, parallel experimental design was used. The jump rope exercise intervention took place during the months of March – June during the school year. Blood samples, anthropometrics, and vascular function parameters were assessed before (baseline) and after the 12-week jump rope exercise program at 8:00 AM (± 1 hour) following an overnight fast. After baseline measurements were performed, the participants were randomly assigned to either the jump rope exercise group (EX, n = 20) or the control group (CON, n = 20). The participants in the EX group participated in an exercise program (50 minutes per day, 5 times per week for 12 weeks) that consisted of jump rope variations. Exercise was performed at 2:00PM (± 1 hour) Monday-Friday. The EX group did not perform any additional exercise outside of this prescribed program during the 12 weeks. The participants in the CON group did not participate in the exercise intervention, or any outside exercise during the 12-week period, but were present and supervised in the laboratory at the same frequency, duration, and time of day as the EX group throughout the entire study period. Both groups of participants were advised weekly not to change their diet habits (~1920 kcal/day) for the duration of the study, and diet logs were obtained every week to keep track of dietary intake. Water intake was not recorded, however, participants were encouraged to consume approximately 2.5 liters of water per day (Sawka et

al. 2005). All exercise sessions were supervised by trained professionals and all measurements were taken by qualified researchers.

Blood sampling and analysis

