Anthropometric measurements were taken at baseline and after 12 weeks. Height was measured without shoes using a stadiometer to the nearest 1.0 cm. Body composition was measured using bioelectrical impedance analysis (BIA) (InBody 230, Biospace, Seoul, Korea), which simultaneously recorded total body mass (nearest 0.1kg), percent body fat (nearest 0.1%), and fat-free mass (nearest 0.1 kg) (Seo et al. 2012). The InBody 230 specifically has been validated to be consistent with the doubly labeled water method (Beato et al. 2018) and dual x-ray absorptiometry for measurements of total fat mass, total lean mass, and percent body fat (Karelis et al. 2013). For BIA, the intra-assay coefficient of variation (repeated measures within individual) was $0.8 \pm 0.9\%$ and the inter-assay coefficient of variation (repeated measures between different days) was $0.3 \pm 0.2\%$. BMI was calculated as body mass divided by the square of height (kg/m^2). Waist circumference was recorded using a standard tape measure to the nearest 0.1 cm

at the midpoint between the iliac crest and the lower rib. These values were used to determine adiposity in absolute terms; however, there are no standard values that are considered to represent high adiposity in children and adolescents (Flegal et al. 2010).

Vascular function

Resting systolic and diastolic BP (mmHg) and resting heart rate (bpm) were both measured in duplicate using an automatic sphygmomanometer (HEM-7113 INT; Omron Corp., Kyoto, Japan) and radial artery palpation, respectively, at baseline and after 12 weeks. The measurements were recorded after participants were in a seated position for 5 minutes. The average of the two measurements was recorded as the resting BP and resting heart rate. Brachial-to-ankle pulse wave velocity (baPWV, m/s), an indicator of peripheral arterial stiffness, was measured using applanation tonometry (SphygmoCor CPV system, AtCor Medical Ltd, Sydney, Australia), followed by data analysis (version 8.0, SphygmoCor Cardiovascular Management Suite, AtCor Medical Ltd, Sydney, Australia). Two measurements were collected, one at each time point, and averaged as previously described (Weber et al. 2004; Yambe et al. 2007).

Jump rope exercise program

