The Shapiro-Wilk test was used to determine the normality of the data. Independent t-tests were used to determine baseline differences between the two groups. A two-way analysis of variance (ANOVA) with repeated measures [group (CON and EX) x time (before and after 12 weeks)] was used to compare the difference of changes between pre- and post-jump rope exercise program within and between groups on the dependent variables. Bonferroni correction was used to determine the effects of the jump rope training program over time. When a significant main effect or interaction was noted, paired t-tests were used for post-hoc comparisons. An effect size analysis was performed using eta-squared (η^2) for the two-way ANOVA, and interpreted 0.01, 0.06, and 0.14 as small, medium and large, respectively (Lee et al. 2018). Cohen's d was used for the t-tests, interpreted as 0.20, 0.50, and 0.80 as small, medium and large, respectively (Lee et al. 2018). All analyses were performed using SPSS 25.0 (SPSS Inc., Chicago, IL, USA). Data are presented as Mean \pm SD. Statistical significance was set at $P \leq 0.05$. It was estimated that 40 participants would enable 80% power to detect a 5% decrease in baPWV after the jump rope exercise program based on previous literature (Figueroa et al. 2011).

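### Make the baseline-adjusted EX minus CON difference the test of effect: the planned group x time ANOVA is a change-score comparison, usually less precise than ANCOVA, and it opens within-arm tests; drop the baseline t-tests

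*Combined protocol and SAP*

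**What the plan says.** The Statistical analysis plan specifies "A two-way analysis of variance (ANOVA) with repeated measures [group (CON and EX) x time (before and after 12 weeks" with one value before and one after the programme. Its stated purpose is "to compare the difference of changes between pre- and post-jump rope exercise program within and between groups on the dependent variables", so within-arm and between-arm changes stand side by side and neither is named as the test of effect. Two further sentences lean towards the within-arm reading: "Bonferroni correction was used to determine the effects of the jump rope training program over time" and "When a significant main effect or interaction was noted, paired t-tests were used for post-hoc comparisons". A time main effect is therefore enough to open paired testing within an arm.

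On baseline, the plan says "Independent t-tests were used to determine baseline differences between the two groups". It attaches no action to the result and nowhere uses baseline as a covariate. The Study design section says that blood, anthropometric and vascular measures were all taken before the programme, and that "After baseline measurements were performed, the participants were randomly assigned" to EX or CON, 20 in each.

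**The concern.** There are three linked points, in order of weight.

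1. **The test of effect is not fixed.** The supervised control arm is there to remove anything that moves both arms alike, such as growth, repeated attendance, diet advice, or regression to the mean after selection on raised blood pressure and waist. A paired t-test in EX alone gives up that protection. A shared fall can then be reported as an effect of jump rope because it reached significance in one arm and not in the other.

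2. **Precision is left unused.** Analysing change fixes the slope of the week-12 value on baseline at 1, whereas ANCOVA estimates it. When the true slope is rho, the change score leaves (1 - rho) times any chance baseline gap in the estimate. With 20 per arm such gaps are not small.

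3. **The baseline t-tests answer no useful question.** Allocation followed the baseline measurements and was random, so any difference between arms is due to chance by construction. This is minor taken alone.

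**Working it through.** **Inputs.** From the documents: 20 per arm; one baseline and one week-12 value; significance at 0.05 (taken as two-sided); 80% power claimed for a 5% fall in baPWV. Not in the documents: the SD of baPWV, the pre-post correlation rho, and the size of any time trend shared by the arms. These are varied as assumptions.

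**The plan's own power figure.** It cannot be reproduced without an SD. Read as a between-arm difference tested with 38 df, 80% power needs a standardised effect of 0.909. That implies an SD of the analysed quantity of 5/0.909 = 5.5% of baseline. Nothing in the documents confirms or refutes this. The comparison below is therefore relative: set the interaction test at 80% and ask what ANCOVA would have.

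**Step 1: the interaction is a change-score test.** In a simulated data set of 20 v 20, F(interaction) = 0.04158 and the squared t from a two-sample t-test on change = 0.04158. The identity is exact with two time points.

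**Step 2: relative precision.** In units of the outcome variance, with equal pre and post variances:

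- change score: 2(1 - rho)
- ANCOVA: (1 - rho²) x 37/36, where 37/36 is the average cost of estimating the slope at N = 40
- ratio, ANCOVA to change score: (1 + rho)/2 x 37/36

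Power for ANCOVA uses the noncentral t with 37 df, averaged over the chance baseline imbalance, at the effect that gives the interaction test 80%. The last column is (1 - rho) x 0.3, the error left by a chance gap of 0.3 SD. The SD of that gap is sqrt(2/20) = 0.32 SD, so 0.3 is an ordinary value.

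| rho | Variance ratio | ANCOVA power | Error left by a 0.3 SD gap |
|---|---|---|---|
| 0.5 | 0.771 | 89.0% | 0.15 SD |
| 0.7 | 0.874 | 85.0% | 0.09 SD |
| 0.8 | 0.925 | 82.9% | 0.06 SD |
| 0.9 | 0.976 | 80.9% | 0.03 SD |
| 0.95 | 1.002 | 79.9% | 0.015 SD |

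The last column is not a further harm. Since 2(1 - rho) - (1 - rho²) = (1 - rho)², the excess variance of the change score is exactly the variance contributed by the leftover gap.

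Break-even is where (1 + rho)/2 x 37/36 = 1, so rho = 72/37 - 1 = 0.946. The largest possible loss is 37/36 - 1 = 2.8% in variance.

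In 100,000 simulated null trials per rho, type I error was 4.9% to 5.0% for the change score and 4.9% to 5.1% for ANCOVA. Both tests are valid.

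**Step 3: outcomes used for eligibility.** The Participants section selects on blood pressure ("All participants were classified as prehypertensive (120-140 mmHg systolic BP and/or 80-90 mmHg diastolic BP"), waist and BMI, which may narrow the baseline spread. With an assumed slope of 0.7, residual variance 0.51 and baseline variance v, the ratio is 0.51/(0.09v + 0.51) x 37/36. It is 0.874, 0.944 and 0.984 at v = 1, 0.5 and 0.25, so the gain falls from 13% to 6% or 2%.

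**Step 4: the route into paired tests.** Assume no treatment effect and an equal true fall in both arms. Paired tests are opened when time or interaction has P <= 0.05. The event counted is EX significant, CON not significant, and interaction not significant.

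| Shared fall (SD of change) | Time effect significant | EX-only result |
|---|---|---|
| 0.3 | 46% | 13.5% |
| 0.4 | 70% | 19.4% |
| 0.5 | 87% | 21.2% |
| 0.6 | 96% | 17.6% |

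Outside that window the rate is lower: about 1.5% with no shared fall, 2.7% at 0.1, 6.8% at 0.2, 5.8% at 0.8 and 0.8% at 1.0. If the Bonferroni wording means that each paired test uses 0.025, the rates at 0.3 to 0.6 are 10.6%, 17.3%, 21.8% and 21.5%, so that correction does not remove the problem.

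**The case against.** The strongest reply is that nothing here is invalid. The interaction is an unbiased between-arm test with the right type I error, the plan does speak of a difference of changes between groups, and the paired tests are labelled post hoc. On this view ANCOVA is a preference, and its benefit is unknown because no correlation is given. At rho 0.8 to 0.9 it is worth only 2.9 to 0.9 points of power. For body composition it may be nil: the Anthropometrics section reports that "the inter-assay coefficient of variation (repeated measures between different days) was" 0.3%, which hints at a high rho, although repeatability between days does not by itself give a 12-week correlation. The EX-only rate peaks at the shared falls tabulated first, and in every counted trial a reader who looked at the interaction would see that it was not significant. Finally, the document is written in the past tense and dated 03/25/2019, so true pre-specification may no longer be possible.

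Much of this stands. The gain is one of efficiency, it varies by outcome, and the paired-test problem is concentrated at moderate shared trends. It does not remove the point. The plan never ranks the between-arm contrast above the within-arm one, and it treats a time main effect as equal to an interaction in opening paired tests. The precision trade is also lopsided: up to about 9 points of power gained over the range shown, against about 0.1 point lost at rho 0.95.

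**Conclusion.** The concern holds. This is a recommended improvement, not the correction of an invalid test. The more serious weakness is that no between-arm difference is named as the test of effect while a time effect alone opens within-arm testing. Under a shared fall of 0.3 to 0.6 SD of change this produces a misleading EX-only pattern in 14% to 21% of trials; at 0.2 SD or less, or 0.8 SD or more, the rate is about 1% to 7%. The size of any shared trend is an assumption.

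The gain from ANCOVA is a variance reduction of 23% to 2% for rho from 0.5 to 0.9, and nothing at 0.95. It rests on an assumed rho and equal pre and post variances, and may be smaller where eligibility narrows the baseline range. The algebra is firm; the benefit for any one outcome in this trial cannot be stated from the documents. The baseline t-tests alter no planned inference and are a minor part of the point.

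**What to change.** - For each outcome, specify ANCOVA of the week-12 value on group with that outcome's own baseline as covariate, whatever imbalance is observed.
- Name the adjusted EX minus CON difference, with its 95% CI, as the test of effect. Present within-arm changes as description only, in place of the paired t-tests.
- Replace the baseline t-tests with a table of means and SDs by arm, without P values.
- If the analysis has already been done, rerun it this way, say that the change was made after the fact, and show it beside the planned ANOVA.

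The cost is SAP wording, a different SPSS procedure, one degree of freedom, about 3% variance inflation from estimating the slope (37/36), and the assumption of a linear slope common to both arms. A late change also means reporting two analyses. No new data are needed.

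### The planned repeated-measures ANOVA compares unadjusted changes in girls who have both values; adjusting the 12-week value for baseline is more precise, and it removes bias if loss depends on baseline.

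*Combined protocol and SAP*

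**What the plan says.** The section Statistical analysis plan names one method for the between-group comparison: "A two-way analysis of variance (ANOVA) with repeated measures [group (CON and EX) x time (before and after 12 weeks". It says that this "was used to compare the difference of changes between pre- and post-jump rope exercise program within and between groups". After a significant main effect or interaction, "paired t-tests were used for post-hoc comparisons". Baseline differences between arms are tested by independent t-tests, but nothing is said about using baseline as a covariate. On software, the section says "All analyses were performed using SPSS 25.0", without naming the procedure.

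Under Study design, blood, anthropometric and vascular measures "were assessed before (baseline) and after the 12-week jump rope exercise program", with no visit in between. "After baseline measurements were performed, the participants were randomly assigned", to "the jump rope exercise group (EX, n = 20) or the control group (CON, n = 20").

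The documents give no analysis set, no as-randomised rule, no handling of a missing 12-week value and no dropout allowance. They report no missing value.

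**The concern.** With two time points, the group-by-time term is the difference between arms in mean change. Two consequences follow.

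- A girl without a 12-week value has no change score. She drops out of this test and of the paired t-tests. Because no rule is written, the method sets the analysis population by default: girls with both values.
- Change scores depend on baseline. At a pre-post correlation ρ below 1, girls who start high tend to fall and girls who start low tend to rise, whatever their arm. If the girls left in one arm differ at baseline from those in the other, the difference in change includes this regression to the mean. With complete data, chance baseline imbalance adds noise in the same way.

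Entry required raised blood pressure, so regression to the mean is a live issue for at least that outcome. The exercise arm asks inactive girls for 60 sessions (5 per week for 12 weeks) of rising intensity, so loss related to baseline status is conceivable. At stake are the validity of the randomised comparison if girls are lost, and precision even if none are.

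**Working it through.** **Inputs.** From the documents: 20 per arm, two measurement times, significance at 0.05 (two-sided assumed), and 80% power for a 5% decrease in baPWV. Assumed, because the documents give no figure: ρ of 0.5 to 0.8, equal SD at both times, and loss of 2 or 4 of 20 (10% or 20%) in the exercise arm only. The unit is the baseline SD.

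**The plan's own figure.** The 80% power cannot be reproduced, because no SD is given. In a two-sample t-test with 38 df, 80% power needs a noncentrality of 2.875. The standardised effect is then 2.875 × √(2/20) = 0.909, which implies an SD of change of 5/0.909 = 5.50% of baseline. The steps below take the 80% as given.

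**Precision with complete data**, n = 20 per arm:

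- Change score (the planned test): variance 4(1−ρ)/n.
- Adjusted for baseline: variance 2(1−ρ²)/n.
- Ratio: 2(1−ρ²)/[4(1−ρ)] = (1+ρ)/2.
- Adjusted power when the planned test has 80% (normal approximation): Φ(2.802/√((1+ρ)/2) − 1.96).

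| ρ | Change-score variance | Adjusted variance | Ratio | Adjusted power |
|---|---|---|---|---|
| 0.5 | 0.100 | 0.075 | 0.75 | Φ(1.275) = 90% |
| 0.7 | 0.060 | 0.051 | 0.85 | Φ(1.079) = 86% |
| 0.8 | 0.040 | 0.036 | 0.90 | Φ(0.993) = 84% |

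Allowing for the estimated slope (variance inflation of about 37/36) and the lost degree of freedom lowers these powers to about 89%, 85% and 83%.

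**Bias when loss depends on baseline.** With no true effect, expected change given baseline x is −(1−ρ)(x − μ). If the remaining exercise girls have a mean baseline lower than control by δ, the change-score estimate is biased by (1−ρ)δ. The adjusted estimate removes this term.

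I simulated 20,000 trials per setting, with no true effect. The exercise girls removed were those ranking highest on baseline plus noise of 1 SD.

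| ρ | Lost | δ | (1−ρ)δ | Change-score bias (type I error) | Adjusted bias (type I error) |
|---|---|---|---|---|---|
| 0.5 | 2 | 0.127 | 0.064 | 0.063 (5.5%) | −0.001 (4.9%) |
| 0.5 | 4 | 0.231 | 0.116 | 0.114 (6.6%) | −0.001 (4.9%) |
| 0.7 | 2 | 0.128 | 0.038 | 0.039 (5.3%) | 0.000 (5.0%) |
| 0.7 | 4 | 0.234 | 0.070 | 0.070 (5.7%) | 0.001 (4.9%) |

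The effect the trial is sized for is 0.909 × √(2(1−ρ)) baseline SD, which is 0.909 at ρ = 0.5 and 0.704 at ρ = 0.7. The bias is therefore between 0.039/0.704 = 6% and 0.114/0.909 = 13% of that effect. Losing high-baseline exercise girls hides benefit on outcomes where a fall is good; losing low-baseline girls exaggerates it.

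**Loss that depends on an unseen value** (same settings, absolute bias across the four combinations):

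| Loss depends on | Change score | Adjusted |
|---|---|---|
| 12-week value | 0.04 to 0.12 | 0.07 to 0.18 |
| Change | 0.10 to 0.24 | 0.09 to 0.18 |

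**Where the gain comes from.** In a mixed model with a common baseline mean, the likelihood factors into a baseline part shared by both arms and a part for the 12-week value given baseline and arm. The treatment effect sits only in the second part, which a girl with only a baseline value does not enter. A maximum-likelihood fit with 5 girls missing gave 0.235508 from this model and 0.235508 from ANCOVA in completers.

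**The case against.** The strongest reply is that nothing has been shown to go wrong. No lost girl is reported. Under Study design, control girls attended the laboratory as often and as long as the exercise girls, so visit burden was matched. Exercise sessions were supervised by 5 trainers with 4 girls each. This stands: the bias is conditional on loss that the documents do not show. The sizes are also modest. A bias of 0.04 to 0.12 SD compares with a simulated sampling SD of 0.25 to 0.33, and type I error stays below 7%. The SPSS procedure is not named, so dropping incomplete cases is the usual behaviour of the named method and not a stated rule.

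Three stronger readings are tempting and fail.

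- A reader might infer that a mixed model rescues the comparison by keeping all 40 girls. With one follow-up it does not, as the factorisation shows. A mixed model with separate baseline means does use the baseline-only girls, but it gains little: at 20% missing at random, its variance is 1% to 7% lower than the ANOVA's for ρ from 0.9 to 0.3. With complete data it reproduces the ANOVA interaction test. The common-baseline model does not.
- A reader might infer that adjustment is better under any loss. If loss depends on the 12-week value, it is the more biased of the two.
- A reader might charge lost power to the ANOVA. If 20 per arm gives 80%, power falls to 75.5% at 18 per arm, or to 77.7% with 18 exercise and 20 control girls. That is the cost of missing data, and adjustment does not restore the missing values.

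The complete-data precision argument is untouched by any of this.

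**Conclusion.** The point holds as a weakness in the choice of analysis. The planned test is an unadjusted change-score comparison in girls with both values, although every girl's baseline is already measured.

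- **Complete data:** it is less precise than the adjusted comparison, by a variance ratio of (1+ρ)/2. In power this is about 80% against 84% to 90% for ρ from 0.8 to 0.5, a point or so less after small-sample correction.
- **Loss related to baseline in the exercise arm:** it is biased by about 0.04 to 0.12 baseline SD, against essentially none after adjustment, for 10% to 20% loss and ρ of 0.5 to 0.7.
- **Loss depending on unseen outcomes:** both are biased, and the ranking turns on the mechanism.

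The correlation, the loss rate, the loss mechanism and the 80% starting power are assumptions. The documents do not support saying that this trial's result is biased. The change should be made, but the point does not invalidate the trial.

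**What to change.** Make the primary between-group comparison the 12-week value adjusted for baseline by ANCOVA, reported as an adjusted difference with its 95% confidence interval. A mixed model with a common baseline mean is equivalent here. State that girls are analysed in their assigned arm, and that girls who stop attending sessions are still invited to the 12-week measurements. That second step matters because no model repairs loss that depends on the unseen value. Report the number with a 12-week value in each arm, and keep the repeated-measures ANOVA as a sensitivity analysis.

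The cost is SAP wording and a different procedure in the same software, with no new data item. The adjusted test will not reproduce the ANOVA interaction p-value exactly, so the order of the two analyses should be fixed in writing. The document is written in the past tense. If results have already been seen, report the adjusted analysis as a later addition beside the planned one. If all 40 girls were measured at 12 weeks, saying so settles the missing-data part and leaves only the precision argument.

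### No primary outcome is named, the Bonferroni correction has no stated family across outcomes, and a main effect alone can open pre-post paired t-tests

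*Combined protocol and SAP*

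**What the plan says.** All of the analysis text is in the section headed Statistical analysis plan.

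- **Model.** A repeated-measures ANOVA, "group (CON and EX) x time (before and after 12 weeks", is applied "within and between groups on the dependent variables". The dependent variables are neither listed nor ranked, and no outcome is called primary or secondary anywhere in the document.
- **Multiplicity.** One sentence: "Bonferroni correction was used to determine the effects of the jump rope training program over time". No divisor or set of comparisons follows.
- **Post-hoc rule.** "When a significant main effect or interaction was noted, paired t-tests were used for post-hoc comparisons".
- **Threshold.** "Statistical significance was set at" P ≤ 0.05. No other level is given.
- **Sample size.** Forty participants are said to give "80% power to detect a 5% decrease in baPWV". This is the only sentence that singles out an outcome.

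The sections on blood sampling, anthropometrics and vascular function describe the variables measured at both visits.

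**The concern.** A reader cannot tell which result decides the trial, or at what error rate. baPWV is the natural candidate, but no analysis sentence gives it priority, so nothing stops another outcome from being presented as the main finding.

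The Bonferroni sentence does not fill the gap. With two time points there is one pre-post contrast per arm, so the natural divisor is 1 (no correction), or 2 if both arms' paired tests are counted. Neither deals with the number of outcomes.

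The post-hoc rule adds a second problem. Its trigger is a main effect *or* an interaction, so a change over time common to both arms is enough to open the paired tests. A paired pre-post test does not compare the arms. If it is significant in the exercise group (EX) and not in the control group (CON), that is easily read as a program effect although no between-arm difference has been shown.

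**Working it through.** **Inputs from the documents.** 20 per arm (Study design); significance at 0.05; trigger for post-hoc tests as written; 80% power for a 5% fall in baPWV (all Statistical analysis plan).

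**Count of variables measured twice.**
- Blood: nitrate/nitrite, ET-1, CRP = 3.
- Anthropometrics: body mass, percent fat, fat-free mass, BMI, waist = 5. Height is also in this section, which says "Anthropometric measurements were taken at baseline and after 12 weeks". It is left out here because it is not a plausible target of the program.
- Vascular: systolic BP, diastolic BP, heart rate, baPWV = 4.
- Total 3 + 5 + 4 = 12, or 13 with height.
- A narrower set suggested by the title (vascular health and inflammatory markers): baPWV, systolic BP, diastolic BP, nitrate/nitrite, ET-1, CRP = 6.

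**Assumed, because the documents give no figures.** Correlations between outcomes, a within-person pre-post correlation of 0.7, and the size of any change shared by both arms.

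**1. The plan's own figure.** No SD is given, so the power statement can be neither reproduced nor refuted. In a 2 x 2 mixed ANOVA the group x time F-test equals a two-sample t-test on change scores with 2 × 20 − 2 = 38 df. By noncentral t, 80% power at two-sided 0.05 needs d = 0.909. A 5% fall then implies an SD of percent change of 5/0.909 = 5.5.

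**2. False-positive interactions across outcomes.** No program effect, each outcome tested at 0.05. Under independence the chance of at least one is 1 − 0.95^m:
- m = 6: 1 − 0.95^6 = 0.265
- m = 12: 1 − 0.95^12 = 0.460

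Simulation (100,000 trials, equal correlation between outcomes):

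| Correlation | 0 | 0.3 | 0.5 | 0.7 |
|---|---|---|---|---|
| 6 outcomes | 0.264 | 0.241 | 0.209 | 0.168 |
| 12 outcomes | 0.455 | 0.400 | 0.325 | 0.234 |

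The zero-correlation column for 12 outcomes is a ceiling, not a realistic value. BMI is computed from body mass and height, and three body-composition measures come from one impedance reading.

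**3. The post-hoc rule as written, per outcome.** Simulation of pre and post values (200,000 trials). The rule opens when the time, group or interaction test has P ≤ 0.05, and both arms have the same true change. Proportion of trials with EX significant and CON not:

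| Shared change (SD of change) | 0 | 0.2 | 0.3 | 0.4 |
|---|---|---|---|---|
| Rule as written, paired tests at 0.05 | 0.031 | 0.090 | 0.159 | 0.221 |
| Rule as written, paired tests at 0.025 | 0.019 | 0.065 | 0.126 | 0.197 |
| Interaction required first, 0.05 | 0.016 | 0.020 | 0.022 | 0.024 |
| Interaction required first, 0.025 | 0.010 | 0.016 | 0.020 | 0.023 |

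The 0.025 rows are the generous reading of Bonferroni (divisor 2). They do not remove the problem; the interaction requirement largely does.

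**4. What each term tests.** Randomisation follows the baseline measurements, so with no program effect both the group main effect and the interaction have about 5% type I error. The group main effect averages pre and post, which halves the effect. At d = 0.909 and pre-post correlation 0.7, the SD of change is √(2 × 0.3) = 0.775 and the SD of the pre-post average is √((1 + 0.7)/2) = 0.922. The standardised group effect is therefore 0.909 × 0.775 / 2 / 0.922 = 0.38, with about 22% power against 80% for the interaction. The time main effect and the paired tests do not compare the arms at all.

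**5. Cost of correcting the other outcomes.** An effect with 80% power at 0.05 (d = 0.909) has power 0.569 at 0.05/5 and 0.454 at 0.05/11.

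**The case against.** - *The right test is already in the plan.* True: the ANOVA contains the interaction and would report it. The text permits misuse of the paired tests; it does not plan it. What stands is that the plan does not reserve treatment claims for the interaction and states a trigger that bypasses it.
- *baPWV is identifiable as the primary.* Fair, since the study is sized on it. But it is unlabelled, and no analysis sentence gives it precedence.
- *The 9-22% depends on a shared change that nobody has shown.* Correct. The documents give no size. Regression to the mean applies mainly to blood pressure, on which participants were selected, and not directly to baPWV or the blood markers. Growth over 12 weeks at ages 14-16 is possible for other variables. With no shared change the rate is about 3% per outcome, below 5%. The issue of many outcomes remains.

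Three stronger readings might be inferred and are not supported.
1. *The trial's error rate is 46%.* That needs 12 independent confirmatory outcomes. The documents do not say which variables are outcomes, and several are derived from one another.
2. *Only the interaction is a valid test of the program.* The group main effect is also valid; it is diluted.
3. *No pre-post change in baPWV exists.* The Vascular function section says "Two measurements were collected, one at each time point, and averaged as previously described", which taken literally would merge the two visits. The Study design section and the ANOVA both treat before and after as separate, so this is probably loose wording. It adds no weight to this point.

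**Conclusion.** The point holds as stated in the heading, and it should be fixed because the post-hoc rule, followed as written, can produce misleading evidence of a program effect.

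- **Across outcomes:** a chance of about 17-26% of at least one false-positive interaction for the six title outcomes (correlation 0.7 down to 0). For all 12 variables, excluding height, it is about 23-40% (correlation 0.7 down to 0.3). Both assume no correction across outcomes and equal correlation between them.
- **Within an outcome:** EX significant and CON not in about 3% of trials with no change in either arm, and 9-22% with a shared change of 0.2-0.4 SD of change, against about 2% if the interaction must be significant first. The shared change and the pre-post correlation of 0.7 are assumptions.

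That the text names no primary, gives no Bonferroni family and lets a main effect open the paired tests rests on the wording alone, not on these assumptions.

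**What to change.** 1. Name the group x time interaction for baPWV as the single primary test, at two-sided 0.05.
2. Amend the post-hoc sentence so that a significant group x time interaction is the only trigger, and describe the paired t-tests as descriptive follow-up. State that main effects and within-group tests do not support a treatment claim.
3. Keep the Bonferroni sentence, but state its divisor and the comparisons it covers. List the other outcomes and label them secondary or exploratory. If claims on them are wanted, state one multiplicity procedure across their interaction tests, for example Holm, carried out only if baPWV is significant.
4. The document is written in the past tense. If the data were already analysed, date these designations and disclose them as post hoc. They do not restore a prespecified 5% error rate, but the restriction on treatment claims still applies.

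**Cost.** Text only; no new data and no adjustment of alpha for the primary test. The other outcomes lose confirmatory status or, if claims on them are kept, power: 80% falls to about 57% at the first Holm step with 5 other outcomes and about 45% with 11.

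**Separate clarity point.** Reword the baPWV averaging sentence under Vascular function so that one pre and one post value are clearly described, in line with the Study design section and the ANOVA.
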